5.2 SAFETY PARAMETERS AND DEFINITIONS

Safety assessments will consist of monitoring and recording adverse events, including serious adverse events; measurement of protocol-specified safety laboratory assessments; and other protocol-specified tests that are deemed critical to the safety evaluation of the study.

Certain types of events require immediate reporting to the Sponsor, as outlined in Section 5.4.

5.2.1 Adverse Events

According to the ICH guideline for Good Clinical Practice, an adverse event is any untoward medical occurrence in a clinical investigation subject administered a pharmaceutical product, regardless of causal attribution. An adverse event can therefore be any of the following:

- Any unfavorable and unintended sign (including an abnormal laboratory finding), symptom, or disease temporally associated with the use of a medicinal product, whether or not considered related to the medicinal product
- Any new disease or exacerbation of an existing disease (a worsening in the character, frequency, or severity of a known condition)
- Recurrence of an intermittent medical condition (e.g., headache) not present at baseline
- Any deterioration in a laboratory value or other clinical test (e.g., ECG, X-ray) that is associated with symptoms or leads to a change in study treatment or concomitant treatment or discontinuation from study drug
- Adverse events that are related to a protocol-mandated intervention, including those that occur prior to assignment of study treatment (e.g., screening invasive procedures such as biopsies)

5.2.2 Serious Adverse Events (Immediately Reportable to the Sponsor)

A serious adverse event is any adverse event that meets any of the following criteria:

- Fatal (i.e., the adverse event actually causes or leads to death)
- Life threatening (i.e., the adverse event, in the view of the investigator, places the patient at immediate risk of death)
- This does not include any adverse event that had it occurred in a more severe form or was allowed to continue might have caused death.
- Requires or prolongs inpatient hospitalization
- Results in persistent or significant disability/incapacity (i.e., the adverse event results in substantial disruption of the patient's ability to conduct normal life functions)
- Congenital anomaly/birth defect in a neonate/infant born to a mother exposed to study drug
- Significant medical event in the investigator's judgment (e.g., may jeopardize the patient or may require medical/surgical intervention to prevent one of the outcomes listed above)

The terms “severe” and “serious” are not synonymous. Severity refers to the intensity of an adverse event (rated as mild, moderate, or severe, or according to NCI CTCAE criteria; see Section 5.3.2); the event itself may be of relatively minor medical significance (such as severe headache without any further findings).

Severity and seriousness need to be independently assessed for each adverse event recorded on the eCRF.

Serious adverse events are required to be reported by the investigator to the Sponsor immediately (i.e., no more than 24 hours after learning of the event; see Section 5.4 for reporting instructions) via appropriate SAE reporting form.

Related SAEs MUST be collected and reported regardless of the time elapsed from the last study treatment administration, even if the study has been closed.

Unrelated SAEs must be collected and reported during the study and for up to 28 days after the last dose of study medication.

5.3 METHODS AND TIMING FOR CAPTURING AND ASSESSING SAFETY PARAMETERS

The investigator is responsible for ensuring that all adverse events (see Section 5.2.1 for definition) are recorded on the Adverse Event eCRF and reported to the Sponsor in accordance with instructions provided in this section and in Sections 5.4.

For each adverse event recorded on the Adverse Event eCRF, the investigator will make an assessment of seriousness (see Section 5.2.2 for seriousness criteria), severity (see Section 5.3.2), and causality (see Section 5.3.3).

5.3.1 Adverse Event Reporting Period

Investigators will seek information on adverse events at each patient contact. All adverse events, whether reported by the patient or noted by study personnel, will be recorded in the patient’s medical record and on the Adverse Event eCRF.

After informed consent has been obtained **but prior to initiation of study drug**, only serious adverse events caused by a protocol-mandated intervention should be reported

After initiation of study drug, all adverse events, regardless of relationship to study drug, will be reported until 4 weeks (28 days) after the last dose of study drug (End of study/early withdrawal visit)

Resolution of adverse events and serious adverse events including dates should be followed-up until it is known or end of study/early withdrawal visit, whichever occurs first and documented on the Adverse Events eCRF and in the patient’s medical record to facilitate source data verification.

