4.2.2 Dosage, Administration and Compliance

4.2.2.1 Dosage and administration of Recormon®

Injectable solution of Recormon® 30,000 or 60,000 IU per week administered subcutaneously

The initial dose is 30,000 IU per week administered subcutaneously

Response will be firstly evaluated at week 4 (visit 2):

- If haemoglobin level reaches ≥ 12 g/dL at any time, Recormon® should be discontinued until Hb levels are ≤ 10 g/dL
- If the haemoglobin level increases < 1 g/dL from screening level and haemoglobin level < 12 g/dL, a 60,000 IU weekly of Recormon® will be administered subcutaneously until week 12.
- If the haemoglobin level increases ≥ 1 g/dL from screening level and haemoglobin level < 12 g/dL, a 30,000 IU weekly of Recormon® will be continued until week 12

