4.4.2.3 Assessments at End of Study/Early withdrawal visit

End of study/early withdrawal visit will occur at 4 weeks after last dose of Recormon®. This visit will include the following evaluations:

- Physical examination and vital sign measurements
- Safety laboratory assessments (see section 4.4.1.4 for details about individual laboratory assays)
- AE recording
- Recording of concomitant treatments and therapies
- Recording of RBC transfusion needed from previous visit

Please see Appendix 1 for the schedule of assessments performed at the end-of-study visit/early termination visit.

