- The Thai Society of Hematology. Guideline for diagnosis and management of Myelodysplastic Syndrome (www.tsh.or.th/files_news/newsFile_20110512140230.doc)

Appendix 1

Schedule of Assessments

	Screening	treatment phase				End-of-Study visit
Visit	S1	V1	V2	V3	V4	F
Week	-2	0	4	8	12	15 ^a
Visit window ± (week)			1	1	1	1
Informed consent ^b	X					
Medical history	X					
Physical examination/vital signs	X	X	X	X	X	X
CBC ^c	X	X	X	X	X	X
Liver function test ^d	X	X	X	X	X	X
Creatinine	X	X	X	X	X	X
Serum EPO	X					
Serum Ferritin	X					X
Serum pregnancy ^e	X					
Record of RBC Transfusion	X	X	X	X	X	X
Concomitant treatment	X	X	X	X	X	X
Adverse event		X	X	X	X	X
Drug dispensing ^f		X	X	X		

^a In case of early discontinuation, end-of-study for safety follow up must be undertaken 4 weeks after the last study drug administration (unless the reason for early withdrawal is withdrawal of consent)

^b Written informed consent is required before performing any study-specific tests or procedures. Signing of the Informed Consent Form can occur outside the 14-day screening period.

^c Parameters will include haemoglobin (Hb), red blood cell count (RBC), white blood cell count (WBC) and differentials, and platelet count

^d Liver function test includes alanine aminotransferase (ALT/SGPT), aspartate aminotransferase (AST/SGOT)

All women of childbearing potential (including those who have had a tubal ligation) will have a serum pregnancy test at screening. Patients who are amenorrhoeic for at least 12 months are not considered of childbearing potential.

^f If haemoglobin level reaches ≥ 12 g/dL at any time, Recormon[®] should be discontinued until Hb levels are ≤ 10 g/dL.

Appendix 2

International Prognostic Scoring System (IPSS)

(Greenberg et.al, 1997)

The 1997 International Prognostic Scoring System (IPSS) for De Novo Myelodysplastic Syndrome

Prognostic Factor	Category Score ^a				
	0 (best)	0.5	1	1.5	2 (worst)

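### The ±1 week window in Appendix 1 lets the end-of-study visit fall up to 7 days before the 28-day adverse event reporting period ends, with no later contact planned

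*Protocol*

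**What the plan says.** Four places in the protocol bear on when adverse event follow-up ends.

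- **Section 5.3.1** requires that, once study drug has started, all adverse events "will be reported until 4 weeks (28 days) after the last dose of study drug", and it then names the end-of-study visit in brackets. The bracket makes day 28 and the visit one and the same point. The same section has investigators ask about adverse events whenever they are in contact with the patient, and it stops follow-up of resolution at this visit if the outcome is not known sooner.
- **Section 5.2.2** has two rules for SAEs: "Unrelated SAEs must be collected and reported during the study and for up to 28 days after the last dose of study medication", and, without a limit, "Related SAEs MUST be collected and reported regardless of the time elapsed from the last study treatment administration".
- **Section 4.4.2.3** fixes the visit with no tolerance: "End of study/early withdrawal visit will occur at 4 weeks after last dose of Recormon". Sections 3.2 and 3.4.2 also give 4 weeks.
- **Appendix 1** puts the visit (column F) at week 15. The visit-window row is empty for S1 and V1 and has an entry of 1 week under V2, V3, V4 and F. There is no column after F. Footnote a says that after early discontinuation "end-of-study for safety follow up must be undertaken 4 weeks after the last study drug administration", again with no window of its own.

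**The concern.** The text treats the visit as happening on day 28, while the schedule that sites work from allows it a week earlier. A visit inside the window can therefore come before the end of the reporting period that the visit is meant to close.

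This has a practical effect because events are collected by asking at contacts, and no contact is planned after column F. No rule asks for a day-28 check when the visit is early. The bracket in section 5.3.1 also lets a site reasonably regard the period as closed once the visit has taken place. Section 5.3.4.5 ties the recording of deaths to the same period, so its end date should not have two readings.

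What is at stake is how completely adverse events are ascertained late after the last dose. Adverse event incidence is the safety outcome (section 3.4.2). An analysis plan cannot recover events that nobody asked about, so the protocol is the place to settle this.

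**Working it through.** **Inputs**

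- Reporting period after the last dose: 28 days (sections 5.3.1 and 5.2.2).
- End-of-study visit: week 15, window ±1 week, so weeks 14 to 16 (Appendix 1).
- Last dose: week 11. This is inferred from weekly dosing starting at week 0 and drug dispensed at V1, V2 and V3 (weeks 0, 4 and 8) but not at V4 (Appendix 1).
- Safety precision statement: 108 evaluable patients, event proportion 0.0274, at least 95% probability of seeing one or more events (section 6.1).

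**Step 1: reproduce the plan's figure.** Days after last dose = (visit week − last-dose week) × 7. For the nominal visit, (15 − 11) × 7 = 28 days. This agrees with the 4 weeks in the text and supports week 11 as the last dose.

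**Step 2: apply the window.**

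| Visit week | Days after last dose | Days short of 28 |
|---|---|---|
| 14 | (14 − 11) × 7 = 21 | 7 |
| 15 | (15 − 11) × 7 = 28 | 0 |
| 16 | (16 − 11) × 7 = 35 | none (7 beyond) |

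For early discontinuers, 4 weeks ±1 week also gives days 21 to 35. This holds only if the column F window applies to them, which footnote a does not say.

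**Step 3: express the gap.**

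- Share of the post-dose period: 7 / 28 = 25%.
- Whole adverse event period from first dose: 11 × 7 + 28 = 105 days. Share: 7 / 105 = 6.7%.

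**Step 4: bound the effect on the safety result.** First the plan's own figure: 1 − (1 − 0.0274)^108 = 0.950, as section 6.1 states. Then an extreme case, with three assumptions that are not in the protocol: the event rate is constant over the 105 days, every patient is seen at the early limit, and nothing from the last 7 days is reported.

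- Proportion with the event in 105 − 7 = 98 days: 1 − (1 − 0.0274)^(98/105) = 0.0256.
- Chance of at least one event in 108 patients: 1 − (1 − 0.0256)^108 = 0.939.

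The proportion falls from 0.0274 to 0.0256, and the probability from 95.0% to 93.9%.

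**Step 5: check the repair.** With a window of 0/+1 week, the visit falls on days 28 to 35, and no attending patient has an uncovered part of the period.

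**The case against.** The strongest reply is that the reporting period is not shortened at all. Section 5.3.1 still obliges investigators to report to day 28 and covers events that patients volunteer as well as those found by staff. Section 5.2.2 keeps unrelated SAEs open to day 28 and related SAEs open indefinitely, and section 5.1 describes continuous monitoring. The text already counts the visit from the last dose, and a ±1 week tolerance is symmetric. All of this stands, and it limits the loss to a planned prompt for non-serious adverse events and unrelated SAEs. It does not remove the mismatch: one rule allows the closing visit on day 21, another makes that visit the end of a 28-day period, and nothing bridges the two.

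Four stronger readings may tempt a reader, and the protocol does not support them.

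- **That up to 14 of the 28 days are lost.** This needs a dose at week 12, read from the wording that "a 30,000 IU weekly of Recormon® will be continued until week 12". Appendix 1 dispenses no drug at V4, and only a last dose at week 11 makes week 15 equal to 4 weeks. What that wording means is a separate question from the visit window.
- **That the safety tables would claim 28 days of observation for everyone.** Section 6.5 says only that incidence is summarised by system-organ class and preferred term, and leaves further detail to the analysis plan.
- **That late events would simply be missed.** The duty to report remains, so under-ascertainment is possible but not certain.
- **That unequal follow-up biases a comparison.** There is one arm. Follow-up may differ between patients, from 21 to 35 days, but no treatment contrast is affected. The repair does not equalise follow-up either; it removes the shortfall.

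**Conclusion.** The mismatch is real and minor. For patients seen before day 28, up to 7 days at the end of the reporting period have no planned contact at which non-serious adverse events and unrelated SAEs are sought. That is 25% of the post-dose period but only 6.7% of the whole period. Patients seen on day 28 or later are unaffected.

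The result rests on a last dose at week 11, on the window entry under column F applying to the end-of-study visit, and on the absence of any scheduled contact after it. How many patients would be seen early cannot be known from the protocol. Even the extreme case moves the detection probability by only about one percentage point (95.0 − 93.9 = 1.1), so no conclusion of the study depends on this. It is worth correcting because two stated rules disagree and the correction is cheap.

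**What to change.** Reconcile Appendix 1 with sections 4.4.2.3, 5.2.2 and 5.3.1 so that the last adverse event contact is not before day 28 after the last dose. Either of these would do it:

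- give column F a window of 0/+1 week counted from the last dose, with week 15 kept only as the nominal position, and state in footnote a that the same window applies after early discontinuation; or
- keep ±1 week and add a telephone check of adverse events on day 28 for any patient whose visit falls earlier.

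With the second option, section 5.3.1 should say that the period ends at day 28 and not at an earlier visit.

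The change amounts to one cell and one footnote in Appendix 1, plus that clause in section 5.3.1 if the second option is chosen. The cost is that some visits fall a few days later or some patients need a call. No dose, treatment rule or endpoint changes.

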5.3.2 Assessment of Severity of Adverse Events

The adverse event severity grading scale for the NCI CTCAE (v4.0) will be used for assessing adverse event severity. Table 1 will be used for assessing severity for adverse events that are not specifically listed in the NCI CTCAE.

Table 1 Adverse Event Severity Grading Scale

Grade	Severity
1	Mild; asymptomatic or mild symptoms; clinical or diagnostic observations only; or intervention not indicated
2	Moderate; minimal, local, or non-invasive intervention indicated; or limiting age-appropriate instrumental activities of daily living ^a
3	Severe or medically significant, but not immediately life-threatening; hospitalization or prolongation of hospitalization indicated; disabling; or limiting self-care activities of daily living ^{b,c}
4	Life-threatening consequences or urgent intervention indicated ^d
5	Death related to adverse event ^d

NCI CTCAE = National Cancer Institute Common Terminology Criteria for Adverse Events.

Note: Based on the NCI CTCAE (v4.0), which can be found at: http://evs.nci.nih.gov/ftp1/CTCAE/CTCAE_4.03_2010-06-14_QuickReference_8.5x11.pdf

^a Instrumental activities of daily living refer to preparing meals, shopping for groceries or clothes, using the telephone, managing money, etc.

^b Examples of self-care activities of daily living include bathing, dressing and undressing, feeding one's self, using the toilet, and taking medications, as performed by patients who are not bedridden.

^c If an event is assessed as a "significant medical event," it must be reported as a serious adverse event (see Section 5.4. for reporting instructions), per the definition of serious adverse event in Section 5.2.2.

^d Grade 4 and 5 events must be reported as serious adverse events (see Section 5.4. for reporting instructions), per the definition of serious adverse event in Section 5.2.2.

5.3.3 Assessment of Causality of Adverse Events

Investigators should use their knowledge of the patient, the circumstances surrounding the event, and an evaluation of any potential alternative causes to determine whether or not an adverse event is considered to be related to the study drug, indicating "yes" or "no" accordingly.

For patients receiving combination therapy, causality will be assessed individually for each protocol-mandated therapy.

5.3.4 Procedures for Recording Adverse Events

Investigators should use correct medical terminology/concepts when recording adverse events on the Adverse Event eCRF. Avoid colloquialisms and abbreviations.

Only one adverse event term should be recorded in the event field on the Adverse Event eCRF.

5.3.4.1 Diagnosis versus Signs and Symptoms

A diagnosis (if known) should be recorded on the Adverse Event eCRF rather than individual signs and symptoms (e.g., record only liver failure or hepatitis rather than jaundice, asterixis, and elevated transaminases). However, if a constellation of signs and/or symptoms cannot be medically characterized as a single diagnosis or syndrome at the time of reporting, each individual event should be recorded on the Adverse Event eCRF. If a diagnosis is subsequently established, all previously reported adverse events based on signs and symptoms should be nullified and replaced by one adverse event report based on the single diagnosis, with a starting date that corresponds to the starting date of the first symptom of the eventual diagnosis.

5.3.4.2 Adverse Events Occurring Secondary to Other Events

In general, adverse events occurring secondary to other events (e.g., cascade events or clinical sequelae) should be identified by their primary cause, with the exception of severe or serious secondary events. However, medically significant adverse events occurring secondary to an initiating event that are separated in time should be recorded as independent events on the Adverse Event eCRF.

5.3.4.3 Persistent or Recurrent Adverse Events

A persistent adverse event is one that extends continuously, without resolution, between patient evaluation timepoints. Such events should only be recorded once on the Adverse Event eCRF. The initial severity of the event should be recorded, and the severity should be updated to reflect the most extreme severity any time the event worsens. If the event becomes serious, the Adverse Event eCRF should be updated to reflect this.

A recurrent adverse event is one that resolves between patient evaluation timepoints and subsequently recurs. Each recurrence of an adverse event should be recorded separately on the Adverse Event eCRF.

5.3.4.4 Abnormal Laboratory Values and Vital Sign Values

Not every laboratory abnormality qualifies as an adverse event. A laboratory test result must be reported as an adverse event if it meets any of the following criteria:

Accompanied by clinical symptoms

Results in a change in study treatment

Results in a medical intervention or a change in concomitant therapy

Clinically significant in the investigator's judgment

It is the investigator's responsibility to review all laboratory findings and vital sign findings. Medical and scientific judgment should be exercised in deciding whether an isolated laboratory abnormality or an isolated vital sign abnormality should be classified as an adverse event.

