5.3.4.6 Preexisting Medical Conditions

A preexisting medical condition is one that is present at the screening visit for this study. Such conditions should be recorded on the General Medical History and Baseline Conditions eCRF.

A preexisting medical condition should be recorded as an adverse event only if the frequency, severity, or character of the condition worsens during the study. When recording such events on the Adverse Event eCRF, it is important to convey the concept that the preexisting condition has changed by including applicable descriptors.

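### Section 5.3.4.4 makes any laboratory result that changes study treatment a mandatory adverse event, with no exception for the planned haemoglobin dose steps; this conflicts with 5.3.4.6 and goes beyond the laboratory-deterioration limb of 5.2.1

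*Protocol*

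**What the plan says.** Four parts of the protocol bear on whether an Hb value goes on the adverse event page.

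- **Section 5.3.4.4** (abnormal laboratory values) sets the reporting rule: "A laboratory test result must be reported as an adverse event if it meets any of the following criteria". There are four criteria: clinical symptoms, a treatment change ("Results in a change in study treatment"), a medical intervention or change in concomitant therapy, and clinical significance in the investigator's view. The section opens with "Not every laboratory abnormality qualifies as an adverse event" and closes by leaving isolated abnormalities to the investigator.
- **Section 5.2.1** defines an adverse event by several alternatives. The one about laboratory values and treatment changes begins "Any deterioration in a laboratory value or other clinical test" and covers deteriorations that bring symptoms or lead to a change or stop of treatment. Another covers unfavourable and unintended signs, abnormal laboratory findings included. Section 5.3 refers to this definition for what is to be recorded: "all adverse events (see Section 5.2.1 for definition".
- **Section 5.3.4.6** states: "A preexisting medical condition should be recorded as an adverse event only if the frequency, severity, or character of the condition worsens during the study". Symptomatic anaemia with Hb below 10 g/dL is an inclusion criterion (4.1.1), so it is present at screening in every patient.
- **Section 4.2.2.1** makes the dose depend on Hb. The step from 30,000 to 60,000 IU weekly applies under the condition "If the haemoglobin level increases < 1 g/dL from screening level and haemoglobin level < 12 g/dL", first evaluated at week 4. Drug is withheld once Hb reaches 12 g/dL.

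The safety outcome in 3.4.2 is how often adverse events occur, of what kind and how severe. Section 6.5 tabulates the incidence of all of them by system-organ class and preferred term.

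**The concern.** In most trials, a laboratory result that leads to a treatment change is a sign of harm, and the criterion in 5.3.4.4 works as intended. Here the dose algorithm is driven by a single laboratory test, and one of its two changes is triggered by too little improvement. Applied as written, the criterion turns an efficacy finding (Hb has not risen enough) into a safety event.

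The study has one arm, so there is no comparison in which such records would show up or cancel out. About eight centres take part, and a site that follows 5.3.4.4 and a site that follows 5.3.4.6 would both be acting in good faith while reporting the same Hb differently. The statistical analysis plan cannot repair this afterwards, because the rule decides what sites enter on the eCRF.

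**Working it through.** The protocol states no figure on this point, so the check is a comparison of the rules, case by case.

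**1. Hb unchanged at week 4, for example 8.5 g/dL at screening and at week 4.**
- 4.2.2.1: the rise is 8.5 − 8.5 = 0 g/dL, below 1 g/dL, and Hb is below 12 g/dL, so the weekly dose changes.
- 5.3.4.4: the result changed study treatment, so reporting is mandatory. The value is also abnormal, so the section's heading does not exclude it.
- 5.3.4.6: the anaemia was present at screening and has not worsened, so it is not recorded.
- 5.2.1, laboratory limb: no deterioration, so not met.

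The conflict is direct.

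**2. Hb up by more than 0 but less than 1 g/dL.** The answers are as in case 1, although the value has improved.

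**3. Hb lower than at screening.** The dose changes and the value has deteriorated. Sections 5.3.4.4 and 5.2.1 agree that it is an event, and 5.3.4.6 can be met through worsening. No conflict.

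**4. Hb reaches 12 g/dL or more.** Withholding drug is a change in study treatment, so the criterion in 5.3.4.4 is met on its wording. There is no deterioration under 5.2.1, and the value may not be abnormal, so the section's heading may exclude it. This is a weaker case.

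**5. Other criteria in 5.3.4.4.** Patients are enrolled for symptomatic anaemia and may already have received transfusions (fewer than 4 units in the 8 weeks before screening, 4.1.1). The criteria on symptoms and on medical intervention can therefore also be met by baseline disease that has not changed.

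**Precedence.** Neither 5.3.4.4 nor 5.3.4.6 says which prevails. The reference in 5.3 to the 5.2.1 definition does not say that it limits the mandatory criteria in 5.3.4.4.

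**Size, as an assumption only.** The protocol gives no share of patients expected to have a planned dose step. Let s be that share, with all 120 planned patients dosed. Patients with such a record = s × 120:
- s = 0.20: 0.20 × 120 = 24
- s = 0.80: 0.80 × 120 = 96

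This is the count if every site followed 5.3.4.4 literally.

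**The case against.** The strongest reply is that the protocol, read as a whole, does not make these values adverse events. Section 5.3 points to the definition in 5.2.1, which rests on untoward occurrences. Section 5.3.4.4 is about abnormal values, says that not all of them qualify, and adds "Medical and scientific judgment should be exercised in deciding whether an isolated laboratory abnormality" or vital sign change counts as an event. Section 5.3.4.6 settles the unchanged anaemia. A sensible investigator would not report it.

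Much of this stands. A reader might infer that every planned Hb step will be counted as an adverse event; the documents do not support that. A rise to 12 g/dL is not a deterioration, and an experienced site may well apply 5.3.4.6. Nor does 5.2.1 as a whole demand deterioration: that is one of its alternatives, so the clean contradiction is with 5.3.4.6.

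The reply does not remove the contradiction. The criteria are mandatory and any one suffices. The sentence on judgment does not say that it overrides them. An Hb of 8.5 g/dL is abnormal, so the heading gives no escape.

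A reader might also try to size the problem from the 0.25 response proportion in 6.1, or set it against the 0.0274 event rate there. Neither works. The 0.25 is a value assumed to illustrate precision, for an endpoint at week 12 (a rise of at least 1.5 g/dL or fewer transfusions), not for a rise below 1 g/dL at week 4; section 1.3 cites response rates of nearly 60–65% in selected patients. The 0.0274 is the rate at which 108 patients give 1 − (1 − 0.0274)^108 = 0.950 probability of seeing a particular event at least once. Extra Hb records do not alter that probability for other events.

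**Conclusion.** The inconsistency is real and should be corrected. For an unchanged low Hb that triggers the week-4 step, 5.3.4.4 requires an adverse event report and 5.3.4.6 rules it out, with no stated precedence. The hold at 12 g/dL is a secondary, weaker example.

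The consequence is possible rather than certain: it depends on which section each site follows. If 5.3.4.4 is followed, lack of response enters the incidence tables as a safety event. The 24 to 96 of 120 patients are the product of an assumed share and carry no evidential weight beyond showing that the effect need not be small. Such records would probably gather in a few identifiable preferred terms, which limits the damage to the detailed tables but not to the overall incidence.

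The primary endpoint and the dose rules are unaffected.

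**What to change.** Add one sentence to 5.3.4.4 and align it with 5.2.1 and 5.3.4.6: an Hb value that only triggers a dose step foreseen in 4.2.2.1, or a cytopenia present at screening that has not worsened, is not an adverse event for that reason alone. Results that have deteriorated, bring new symptoms or are clinically significant stay reportable. Repeat the sentence in the eCRF completion guidance so that all centres apply it alike.

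Also confirm that planned dose changes are recorded on a dosing eCRF. Section 5.3.4.8 names the Study Drug Administration eCRF only for overdose and incorrect administration, so this cannot be taken for granted.

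The cost is one sentence in an amendment and in the guidance. The small downside is that fewer Hb values reach the adverse event page; all remain in the laboratory data, since the blood count is taken at every visit. No dose rule changes.
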